Sample Size. We performed power analyses to detect the effects of CBT-I on primary outcomes [insomnia severity, sleep quality (PSQI), self-reported (PSQI) and actigraph sleep efficiency (SE), and fatigue] with pilot data in which we randomized HF patients to CBT-I (HS) or attention control (HH). We calculated powers to detect differences in changes in outcomes from BL between the two groups to post-intervention (2 wks/T1) with 5% type I error.¹¹⁷ We also calculated powers with scenarios of high within-subjects correlations (Rho=0.6, 0.7, 0.8) for repeated measures during F/U (2 wks, 6, , 12 months) by assuming consistent effect sizes over time¹¹⁸ (Table 3). A sample of 100 independent participants per group will yield $> 90\%$ power to detect CBT-I effects on insomnia severity (ES=0.65), fatigue (ES=0.64), and PSQI sleep quality (ES=0.46) and power of 76.6% for PSQI SE (ES=0.38), but a power of 99.9% for actigraph-measured SE (ES=0.70). In scenarios based on within-subjects correlations of outcomes, we anticipate $> 95\%$ power for most outcomes and $> 80\%$ power for self-reported SE. Inclusion of 200 subjects (100/group) will permit sufficient power to detect the association between improved insomnia severity and symptoms [fatigue ($>99.9\%$, $r = 0.526$), depression (99.16%, $r = 0.299$), anxiety ($> 99.9\%$, $r = 0.510$), and pain (92.7%, $r = -0.238$)]. There will be 92.6% power to detect risk of hospitalization in participants with insomnia remission (9%), compared to no remission (27.8%). We will randomly assign 200 participants in 25-33 clusters of 6-8. Because we do not expect dependency among participants in the same clusters, we will not increase the sample for random cluster assignment.

We computed the power for estimating cost-effectiveness with Willan¹¹⁹ and Glick's¹²⁰ methods, based on an assumed alpha level of 0.05, expected cost difference of \$500, standard deviation for costs of \$2,000, expected correlation between costs and QALYs of -0.1, and willingness-to-pay of \$50,000 per QALY. The expected difference in QALYs, based on the pilot study, is estimated to be -0.33. Together, these values suggest that the sample of 100 subjects/group yields 89.7% power for detecting cost-effectiveness of CBT-I.

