ARES has high sensitivity and specificity¹²³⁻¹²⁵ and better test-retest reliability¹²⁶ than in-lab PSG. We will record 2 nights and calculate respiratory events/total sleep time because of potential night-night variability and score the data through the manufacturer's website with validated automated methods and review by a board certified sleep technician. Although forehead venous pressure distinguished central vs. obstructive respiratory events,¹²³ it is not the gold standard, and we will report only the AHI/RDI. ARES minimizes participant burden and cost, compared with PSG. As in our preliminary study, we will give participants the programmed device and instruction, and they will return it personally or by mail. Drs. [name] and [name] will review scored data and provide patients and referring providers with results/recommendations for follow up.

Randomization/blinding. We will use block randomization to assign participants to groups of 6-8 to assure timely filling of groups and group process. CBT can be provided in groups of 3-12, and groups averaging 5 were used for CBT-I.⁸⁶ As groups complete baseline, we will randomize to treatment assignment with a computer-generated sequence. Recruitment/screening/data collection/data entry personnel will be blinded to group assignment. It is impossible to blind participants, but they will not know the group assignment until the first meeting. Interventionists will be blinded to baseline data and specific hypotheses.

Treatment: CBT-I ("Healthy Sleep" Group: HS). Our manualized protocol includes CBT-I elements (Table 1) in 4 bi-weekly one-hour sessions;^{127,128} a call on alternate weeks; the HS Guide, a workbook with CBT-I components, with sixth grade reading level, print appropriate for older adults, and images reflecting diversity (Appendix); and optional hypnotic tapering. About 80% of hypnotic users selected tapering in our pilot, and we expect hypnotic use to decrease, based on the literature^{81,82} and our experience.²⁰ Four bi-weekly sessions of CBT-I were superior to other frequencies.¹²⁹ The group format was feasible in our pilot, and will enhance social support and learning. Use of a CBT-I trained APRN interventionist is consistent with our²⁹ and other⁹⁴ studies and will promote sustainability due to the greater availability of APRNs than sleep psychologists.

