We will use descriptive statistics to describe clinical and demographic characteristics by treatment group and time. To evaluate differences in insomnia severity, sleep characteristics (Aim 1a), symptoms, PVT (Aim 1b) and functional performance (Aim 2) over the four time points (baseline, 3, 6, and 12 months), we will use GLMM with a repeated measures statement to examine group, time, and group by time effects. Nonlinear time effect will be controlled by transforming a continuous time variable with cube root form, which allows to estimate relatively rapid change in early at post-intervention than the follow-ups. We will choose the best covariance structure (compound symmetry vs. unstructured vs. moving average) by comparing the Akaike Information Criterion (AIC) and Bayesian Information Criterion (BIC). In multivariate models, adjusted intervention effects will be estimated by including covariates that might differ by group assignment (e.g., LVEF, comorbidity, age, SA with CPAP use). We will assess multi-collinearity among covariates with the variance inflation factor (VIF) and eliminate variables with high VIF (> 10) if the intervention effect is not modified after elimination. We will identify influential outliers with DFFITS, DFBETAS, and Cook’s distance. If there are non-normally distributed residuals, the outcome variable will be transformed to ordinal form or fitted with more flexible distributions (e.g., Gamma, Poisson). We will use GEE with a robust working correlation structure to address within-subjects correlations for changes in outcomes with clinical cutoffs (i.e., $ISI \geq$, $ESS \geq 10$, $PSQI \geq 5$, $SMW \geq 1000$) over time. To avoid the inflation of type 1 error, False Discovery Rate (FDR) will be calculated for post-intervention effects on 13 outcome variables. .

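### Therapy groups of 6-8 are randomised and treated as units, but the power calculation and the planned models treat participants as independent

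*Combined protocol and SAP*

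**What the plan says.** The Sample Size section assigns 200 participants in 25-33 clusters of 6-8. It bases power on independence ("A sample of 100 independent participants per group will yield" the listed powers) and sets the clustering aside: "Because we do not expect dependency among participants in the same clusters, we will not increase the sample for random cluster assignment".

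Randomization/blinding confirms that the formed group receives the allocation: "As groups complete baseline, we will randomize to treatment assignment with a computer-generated sequence". The Intervention phase text under Protection of Human Subjects also describes randomisation in groups of 6-8. The Design section speaks of participants being randomised. Read with the other three places, it does not describe individual allocation.

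The CBT-I treatment section gives a reason for group delivery: "The group format was feasible in our pilot, and will enhance social support and learning".

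For the main outcomes the Statistical Analysis Plan says "we will use GLMM with a repeated measures statement to examine group, time, and group by time effects". In that sentence, group means treatment arm. GEE for the dichotomised outcomes addresses within-subject correlation. Neither model has a term for therapy group, and the candidate covariance structures concern repeated measures. The increase from 200 to 240 in Setting/Recruitment is for attrition only.

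**The concern.** When intact groups are allocated and treated together, the information on the arm difference comes from about 25-33 groups, not from 200 separate people. If group members' outcomes are at all alike, the variance of the arm difference exceeds what an individual-level model reports. Confidence intervals are then too narrow and p-values too small for every primary outcome. False discovery rate control does not help, because it takes those p-values as valid inputs.

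The plan offers no evidence for an ICC of zero. It reports no pilot estimate, although the pilot also randomised in groups (of 5), and no sensitivity analysis. Nor could the trial data show the assumption to be wrong under the planned analysis, because therapy group is not in the models. The stated powers also hold only at an ICC of exactly zero, and the two PSQI outcomes have the least margin.

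**Working it through.** **Inputs from the documents.** n = 100 per arm; alpha 5%; group size m = 6-8; effect sizes 0.65 (insomnia severity, ISI), 0.46 (PSQI quality), 0.38 (PSQI sleep efficiency, SE), 0.70 (actigraph SE), 0.64 (fatigue). Sidedness is not stated. A two-sided test reproduces the plan's figures and a one-sided test does not (it gives 85.1% for PSQI SE).

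**Assumption.** ICC 0.01-0.10. The documents give no value.

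**1. Reproduce Table 3 (two weeks post-intervention) under independence.** Power = Φ(d·√(n/2) − 1.96).
- PSQI SE: 0.38 × √50 = 2.687; Φ(0.727) = 76.6% (stated 76.6%).
- PSQI quality: 0.46 × √50 = 3.253; Φ(1.293) = 90.2% (stated 90.2%).
- Fatigue 99.5% (stated 99.5%); actigraph SE 99.9% (99.9%); ISI 99.6% (99.2%).

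The plan's arithmetic is sound. The independence premise is what is in question.

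**2. Add clustering.** Design effect DE = 1 + (m − 1)·ICC. True type I error of the unadjusted test = 2Φ(−1.96/√DE). Power of a test with the correct variance = Φ(d·√(n/(2·DE)) − 1.96).

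Worked case, m = 7, ICC 0.05:
- DE = 1 + 6 × 0.05 = 1.30; effective n = 100/1.30 = 77 per arm.
- Type I error = 2Φ(−1.96/1.140) = 8.6%.
- PSQI SE power = Φ(0.38 × √(50/1.30) − 1.96) = Φ(0.397) = 65%.

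| m = 7 | ICC 0 | 0.01 | 0.05 | 0.10 |
|---|---|---|---|---|
| Design effect | 1.00 | 1.06 | 1.30 | 1.60 |
| Effective n per arm | 100 | 94 | 77 | 63 |
| True type I error | 5.0% | 5.7% | 8.6% | 12.1% |
| Power, PSQI SE | 76.6% | 74% | 65% | 57% |
| Power, PSQI quality | 90.2% | 89% | 81% | 73% |
| Power, ISI | 99.6% | 99% | 98% | 95% |
| Analysed N to keep stated power (200 × DE) | 200 | 212 | 260 | 320 |

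Across m = 6 to 8, type I error is 5.6-5.8%, 8.0-9.2% and 11.0-13.3%. PSQI quality drops below 80% once DE exceeds 1.348, which is an ICC of about 0.07 (m = 6), 0.06 (m = 7) or 0.05 (m = 8). At ICC 0.10 and m = 8, the other three outcomes still have 94.1% (ISI), 93.5% (fatigue) and 96.7% (actigraph SE).

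**3. Simulation check.** With 14 groups of 7 per arm, one visit and 20,000 runs, the unadjusted test rejected a true null in 5.5%, 8.7% and 11.9% of runs at ICC 0.01, 0.05 and 0.10. A cluster-level test held 4.8-5.1%.

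**4. Cost of few groups.** For that layout, a noncentral t on 26 df gives PSQI SE 72.6% and PSQI quality 87.3% even at ICC 0. At ICC 0.01, 0.05 and 0.10 it gives 70%, 61% and 53% for PSQI SE, and 85%, 78% and 69% for PSQI quality.

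**5. Repeated-measures scenario.** Averaging three follow-ups with within-subject correlation ρ gives a variance factor (1 + 2ρ)/3. This reproduces Table 3 to within 2 points. A group effect that is constant over time adds (m − 1)·ICC, which averaging over visits does not reduce. At ICC 0.05, over ρ = 0.6-0.8 and m = 6-8:
- PSQI SE power is 68.3-77.3% (stated 83.0-89.5%).
- PSQI quality power is 83.9-90.7% (stated 94.2-97.3%).
- Type I error is about 8-11%. For example, at ρ = 0.7 and m = 7 the variance ratio is (0.80 + 0.30)/0.80 = 1.375, so type I error is 2Φ(−1.96/√1.375) = 9.5%.

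**The case against.** The size of the problem rests on an assumed ICC. At 0.01 the damage is close to trivial, and nothing in the documents supports 0.10. A benefit of group support that is equal in every group shifts the mean and creates no ICC; groups must differ from one another. Several design features limit such differences: manualised content, one interventionist per condition, fidelity review of 20% of recordings, individual phone calls between sessions, and make-ups with another group or by phone or Skype. The repeated-measures powers, which are nearer the planned analysis, have more room, and PSQI quality stays above 80% there at ICC 0.05. Part of the loss under a cluster-level test comes from fewer degrees of freedom (and from 98 rather than 100 per arm), not from correlation.

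Most of this stands as a limit on magnitude. It does not support an ICC of exactly zero. Groups can still differ in composition, cohesion and calendar time, and the plan's reliance on group process makes zero harder to defend. Make-ups blur membership, but participants are encouraged to stay with their own group, and allocation is by group regardless. In the repeated-measures model the type I inflation is slightly larger than at a single visit.

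**Conclusion.** The concern holds and should be fixed before analysis. The randomised and treated unit appears in neither the power calculation nor the models, so type I error for every primary outcome rests on an untested assumption.

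The harm is conditional: none at ICC 0, small at 0.01, and material from about 0.05. The loss of power matters for PSQI sleep efficiency, which is already below 80% at the two-week visit, and for PSQI quality. For insomnia severity, fatigue and actigraph sleep efficiency, power stays above 90% by design effect up to ICC 0.10, and the issue is the validity of p-values and intervals. These figures assume equal group sizes and the same ICC in both arms. With one interventionist per condition, therapist and arm are also confounded; that is a separate matter which a group term cannot resolve.

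**What to change.** Keep N and change the analysis text.

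1. In each GLMM add a random intercept for therapy group, and a therapy-group-by-visit term if it can be estimated, with Kenward-Roger or Satterthwaite degrees of freedom. Define membership as the group to which the participant was allocated, whatever make-ups were attended.
2. Cluster the GEE on therapy group, with a small-sample-corrected sandwich variance.
3. Resample whole therapy groups in the cost-effectiveness bootstrap.
4. Replace the sentence that assumes no dependency with power restated over ICC 0.01-0.10, and report the estimated ICC with the results.

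**Cost.** SAP wording, one extra random effect, and a therapy-group identifier in the analysis dataset, which the trial needs anyway to run the sessions. With groups of 7, intervals widen by √1.06, √1.30 and √1.60, that is about 3%, 14% and 26% at ICC 0.01, 0.05 and 0.10. Even at ICC 0, the fewer degrees of freedom cost a few points of power. Keeping N restores valid inference but not the stated power: at ICC 0.05, keeping the stated powers would take about 260 analysed participants. The plan should therefore say openly that the two PSQI outcomes may be underpowered.

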We enrolled 52 patients (planned $n = 40$); 48 completed treatment/follow-up in HS ($n = 29$) or HH groups ($n = 19$).²⁸ One HS patient did not complete due to a heart transplant. In the HH, non-completion was due to disappointment with randomization ($n=1$); loss to followup ($n=1$); and change to shift work ($n=1$). Eighty-eight percent of completers had 100% attendance. Inclement weather, damage to home, and death in family and were reasons for missed sessions that were made up by phone. Completers included 23 (47.9%) women, 15 (32.1%) African Americans, and 32 (66.7%) Whites and had NY Heart Class II or III HF. Age was $M = 61.9 \pm 13.3$ (HS group) and 55.2 ± 16.2 years (HH group) ($p = .12$). There were no statistically significant group differences at baseline on gender, NY Heart Class, comorbidity, symptoms or function. The apnea hypopnea index was $M = 7.44 \pm 5.5$ in participants not in treatment for SA. The proportion of patients using positive airway pressure (PAP) was equivalent between groups [$n = 5$ (17%) (HS) and $n = 3$ (16%) (HH)]. OTC or prescribed hypnotics were used 3 or more times/week by $n = 7$ (24%) (HS) and $n = 7$ (37%) (HH); 72% used ACEI/ARBs and 92% used beta-blockers, but there was no statistically significant difference between groups.

Satisfaction and acceptability were high and averaged 7.5-8.7 (scale: 0-10/10= high). Both groups rated scheduling, location, payment, study materials, interventionist effectiveness, and willingness to continue treatment as 8.5-9.5. There were no statistically significant differences between groups on ratings, and participants had no difficulty completing the measures. PAP users reported that CBT-I was helpful.

CBT-I had early and sustained effects. Insomnia severity improved in both groups (T1) and was similar to T1 at T2 (Table 2). The CBT-I effect was moderate-large at T1, with the mean decrease of > 7 points exceeding the criterion for improved function,¹⁰⁵ while the HH decrease was much smaller. In the HS, 93% improved across one or more levels of insomnia severity and only 2 deteriorated, while 68% of the HH group improved, and 26% deteriorated. At T1, only 48% of the HS had any insomnia ($ISI \geq 8$), compared with 68% of the HH group [$OR=0.43$, $CI_{95}=0.13, 1.45$]. The HS group improved at T1 on sleep quality, compared with HH. Self-reported (PSQI) and actigraph SE improved more at T1 in HS, and PSQI SE was similar at T2.

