Exclusion criteria are untreated restless legs syndrome; night/rotating shift work; travel across 2 or more time zones within one month of enrollment; contraindications to sleep restriction [seizure disorder, severe sleepiness (Epworth Scale >18), bipolar disorder]; neurological/musculoskeletal conditions affecting the non-dominant arm (use of wrist actigraph), active illicit drug use, dementia, and end-stage renal failure. Participants who are hospitalized or have emergency department visits, unstable conditions, or changes in vasoactive medications within 4 weeks of recruitment will not be enrolled until 4 weeks elapse without new events. Patients with these events after enrollment will be retained; events will be tracked and included in analyses.

Chronic insomnia and sleep apnea (SA) are often comorbid with HF,¹¹⁰⁻¹¹² but SA was not associated with insomnia in HF patients^{3,8} and did not affect CBT-I outcomes in older adults.⁹⁴ Although positive pressure (PAP) improves some cardiac variables, lack of rigorous long term RCTs preclude widespread SA treatment in HF,¹¹³ and the lower treatment threshold is not well defined.¹¹³⁻¹¹⁵ Most studies were small, poorly controlled, and included patients with moderate-severe SA (apnea hypopnea index/AHI ≥ 15).¹¹⁵ One study (n = 40 completers)¹¹⁶ had participants with AHI > 5 , but mean AHI was ~ 28 , and the proportion with mild SA was not reported. Given limited evidence of PAP benefits in very mild SA, we will include patients with AHI < 10 and refer those with AHI ≥ 10 for further evaluation. Participants with significant SA will be eligible if adherent to PAP ≥ 6 hours/night for at least 3 months. Titration of PAP or sleep studies with PAP use are beyond the study scope, but participants will be eligible if they have insomnia once adherent to PAP. The proportion of PAP users was equivalent between groups in our pilot.

We will track clinical/demographic characteristics [age, gender, race, SA, depression, hypnotics, HF medications (ACEI/ARB, beta blockers), LVEF, NY heart class] and relevant changes at all study milestones and include these indicators in relevant analyses (See data analysis).

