We will run group series simultaneously to offer options for time of day/day of week and offer makeup sessions with another ongoing group, but telephone or Skype make-ups will be used for those unable to attend in person due to weather or other reasons. However, participants will be encouraged to continue with the same group. Make-ups will be held within one week of missed sessions, as in our pilot. Tele-health CBT-I was successful in non-HF patients,¹³⁶ and phone-delivered CBT is efficacious in cardiopulmonary¹⁴⁰ and mental health disorders.^{141,142} We will compare groups on the phone/Skype vs. face-face sessions and attendance and include the number and types of sessions in analyses if groups are unbalanced.

The study is designed to assure treatment fidelity (consistent dose, frequency, and contacts), and we will use similar materials/homework in both manualized conditions (Appendix). We will use protocols we developed to train study personnel. Separate interventionists, blinded to baseline/outcomes data and study hypotheses, will provide both treatment conditions to avoid contamination, and single interventionists will provide each condition. To assure protocol adherence, we will record sessions and script and record phone calls. With published methods,¹⁴³ we will randomly select and evaluate the fidelity of 20% of recordings and give feedback to the therapist. We will promote treatment receipt by reinforcing instruction (return demonstration, workbooks, and phone calls) and providing study information to take home for referral.

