To identify outliers and data errors, we will use logical data checks and handle missing data with the assumption of missing at random (MAR), an approach that assumes missing values have the same patterns as complete data. We will impute missing data on survey items with Rubin’s¹⁹⁴ multiple imputation method, replacing missing values with simulated sets of imputed values from Monte Carlo simulation, and analyze each simulated completed dataset with standard methods. Results will include estimates and confidence intervals that incorporate the uncertainty of imputed values. Generalized Linear mixed Models (GLM) and General Estimating Equations (GEE) allow the use of incomplete repeated measures due to dropout. If there is at least one baseline and follow-up data point. This approach will minimize the effects of sample loss due to attrition

We will compute univariate statistics to examine frequency distributions of categorical variables and normal distributions for continuous variables with box plots and the Shapiro Wilkes test to assess normality. We will test differences in demographic and clinical variables (e.g., SA, LVEF), and baseline adherence, self-care, and self-management (see inclusion/exclusion criteria; clinical/demographic variables) between the two randomized groups to determine the success of randomization. Because some clinical and demographic variables, including PAP use, may influence outcomes, we will include them as covariates in multivariate models if groups are unbalanced on these variables at baseline.

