We will use descriptive statistics to describe clinical and demographic characteristics by treatment group and time. To evaluate differences in insomnia severity, sleep characteristics (Aim 1a), symptoms, PVT (Aim 1b) and functional performance (Aim 2) over the four time points (baseline, 3, 6, and 12 months), we will use GLMM with a repeated measures statement to examine group, time, and group by time effects. Nonlinear time effect will be controlled by transforming a continuous time variable with cube root form, which allows to estimate relatively rapid change in early at post-intervention than the follow-ups. We will choose the best covariance structure (compound symmetry vs. unstructured vs. moving average) by comparing the Akaike Information Criterion (AIC) and Bayesian Information Criterion (BIC). In multivariate models, adjusted intervention effects will be estimated by including covariates that might differ by group assignment (e.g., LVEF, comorbidity, age, SA with CPAP use). We will assess multi-collinearity among covariates with the variance inflation factor (VIF) and eliminate variables with high VIF (> 10) if the intervention effect is not modified after elimination. We will identify influential outliers with DFFITS, DFBETAS, and Cook’s distance. If there are non-normally distributed residuals, the outcome variable will be transformed to ordinal form or fitted with more flexible distributions (e.g., Gamma, Poisson). We will use GEE with a robust working correlation structure to address within-subjects correlations for changes in outcomes with clinical cutoffs (i.e., $ISI \geq$, $ESS \geq 10$, $PSQI \geq 5$, $SMW \geq 1000$) over time. To avoid the inflation of type 1 error, False Discovery Rate (FDR) will be calculated for post-intervention effects on 13 outcome variables.

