Challenges/rationale. Although desirable to include non-English speaking patients, translation is beyond available resources. Inclusion of patients with mild SA is safe and will yield a sufficient sample. We successfully included PAP-adherent SA patients in our pilot, with an equivalent proportion in each group. Attrition was low, but we expect more in a longer study due to HF exacerbation and other events. We will over-recruit and use retention and intent-to-treat strategies. If a patient misses a follow-up, we will follow at the next time point if possible. We will include patients who are stable at B/L and have evidence-based HF disease management because uncompensated HF and/or poor disease management may confound outcomes. Randomization will promote group equivalence, and we will explore possible confounding effects of clinical and demographic factors on the outcome variables. Participants had no difficulty completing the intervention and measures in our pilot and very few participants may be unable to complete the 6MW. Duration of EFS tracking will vary (18-45 months) based on enrollment time but is unavoidable due to total study duration. The five-year study will provide sufficient time to obtain meaningful results. It is possible that HF self-management education may improve health care resource utilization and EFS, but our pilot suggests that CBT-I had a larger effect, and a previous study⁷⁸ showed no effect of HF self-management on this outcome. Comparison of group effects on this outcome is an important goal of the study. Because of the plan for extended follow-up, we will not offer cross-over from the attention-control into the CBT-I condition, and we will track changes in insomnia and self-management behavior over time. The results will be generalizable to HF patients who have chronic comorbid insomnia – approximately half of HF patients.⁸ Future studies will address effectiveness, dissemination and translation of CBT-I into diverse HF settings.

PROTECTION OF HUMAN SUBJECTS

Risks to Human Subjects

a. Human Subjects Involvement and Characteristics

1. Involvement of human subjects

Recruitment & screening:

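### The make-up session rule lets sessions attended and delivery mode enter unspecified analyses when the arms differ on them; an arm comparison adjusted this way is not the effect of assignment, and the plan does not make it supportive

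*Combined protocol and SAP*

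**What the plan says.** The rule stands in the Approach section, in the paragraph on simultaneous group series and make-ups. The arms will be compared on phone or Skype versus in-person "sessions and attendance and include the number and types of sessions in analyses if groups are unbalanced". It names no outcome, no model, no criterion for imbalance, and no primary or supportive status.

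Other places bear on it:

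- **Randomization/blinding:** participants cannot be blinded, but "they will not know the group assignment until the first meeting".
- **Preliminary Studies (pilot):** "In the HH, non-completion was due to disappointment with randomization" in one patient; the other two HH non-completers had different reasons. Also, "Eighty-eight percent of completers had 100% attendance".
- **Challenges/rationale:** "We will over-recruit and use retention and intent-to-treat strategies". The term is not defined further.
- **Data Analysis, repeated in the SAP:** for clinical and demographic variables, "we will include them as covariates in multivariate models if groups are unbalanced on these variables at baseline". For the multivariate models, "adjusted intervention effects will be estimated by including covariates that might differ by group assignment", with examples (LVEF, comorbidity, age, sleep apnoea with CPAP) that do not mention sessions.
- **Approach, tracked characteristics:** the team will record a list that includes depression and hypnotics "and relevant changes at all study milestones and include these indicators in relevant analyses (See data analysis").

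**The concern.** A chance imbalance in a baseline covariate is a sound reason to adjust. An imbalance in sessions is different, because the arm can cause it. Participants learn their arm at the first meeting, so later attendance can respond to it, and a pilot patient left over the allocation. Make-ups by phone or Skype go to people who could not attend in person, and some of the reasons may be linked to prognosis.

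Adjusting for sessions removes any effect of assignment that runs through attendance. It also opens a path through shared causes of attendance and outcome, such as illness. The trigger makes matters worse: it brings the covariate in when the arms differ, which is when adjustment can matter.

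What is at stake is which estimate counts as the trial's result. If the rule fired, a reader could not tell from the documents whether the estimate with or without sessions was the intended one.

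**Working it through.** **1. Does another rule switch this one off?** No. The baseline-imbalance rule cannot cover a session count, which does not exist at baseline, so the make-up rule is separate. The list for the multivariate models is open-ended and neither admits nor excludes sessions. The SAP never mentions sessions. The intent-to-treat phrase does not define an analysis.

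**2. The plan's own figure.** PSQI sleep efficiency, effect size 0.38, 100 per arm, two-sided 5% (sidedness assumed): 0.38 × √(100/2) = 2.687; Φ(2.687 − 1.960) = 76.6%. This matches Table 3, so 0.38 is used below.

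**3. Assumed inputs (not in the documents).** d is the arm difference in sessions, in within-arm SDs. r₀ and r are the within-arm correlations of sessions with outcome at baseline and at follow-up. ρ is the correlation between visits. To show the mechanism: d = 0.5, r = 0.4, ρ = 0.7. These are deliberately unfavourable.

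**4. The planned mixed model.** Data Analysis fits four time points including baseline, with group, time and group-by-time. Sessions are one value per person. Let Δₖ be the unadjusted arm difference at visit k and γ the session coefficient. With a main effect for sessions, the adjusted arm difference at visit k is Δₖ − γd. Group-by-time is then

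(Δₖ − γd) − (Δ₀ − γd) = Δₖ − Δ₀.

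The session term cancels. Simulation with complete data agrees: 0.378 without and 0.378 with sessions; on the cube-root time scale, slope 0.178 and 0.178. With about 20% session-related dropout, 0.387 and 0.388.

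The group main effect does move, by −γd. If sessions relate equally to all four visits, γ = 0.4 and the shift is −0.4 × 0.5 = −0.20. If they relate to the three follow-ups only (compound symmetry), γ = (0 + 3 × 0.4)/4 = 0.3 and the shift is −0.15.

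**5. Other models in which the rule could be applied.**

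| Model | Shift in arm effect | Result from 0.38 |
|---|---|---|
| Follow-up only | −r·d = −0.20 | 0.18 |
| Baseline-adjusted follow-up, r₀ = r | −d·r(1 − ρ)/(1 − r²) = −0.5 × 0.12/0.84 = −0.07 | 0.31 |
| Baseline-adjusted follow-up, r₀ = 0 | −r·d = −0.20 | 0.18 |
| Change score or session-by-time, r₀ = r | −(r − r₀)·d = 0 | 0.38 |
| Change score or session-by-time, r₀ = 0 | −(r − r₀)·d = −0.20 | 0.18 |

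These apply when sessions are in the model. A simulation of the follow-up-only, baseline-adjusted and change-score rows agrees to within 0.01.

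The sign follows r × d. With d = −0.5 and r = 0.4, the follow-up-only effect rises to 0.38 + 0.20 = 0.58. With r = 0 or d = 0 there is no bias.

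**6. Event-free survival.** There is no baseline outcome row to absorb the session term, so the cancellation in step 4 is not available. An early event can itself cut the number of sessions attended. The bias is possible in principle; it has not been quantified.

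**7. How readily would the rule fire?** Taking p < 0.05 as an assumed trigger, the arms must differ by 1.972 × √(2/100) = 0.28 SD. For full attendance around 88%, the gap must be 1.96 × √(0.88 × 0.12 × 2/100) = 9 percentage points. At a true d of 0.1 the rule fires in about 11% of trials, and a follow-up-only effect of 0.38 averages 0.37 to 0.38, which is negligible. The pilot gives attendance for both arms together only. Completion was 29 of 30 versus 19 of 22 (Fisher p = 0.30), but that is study completion, not attendance, and is compatible with no difference.

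**The case against.** The best defence is that the sentence belongs to a section on delivery, not analysis. Data Analysis and the SAP give the group, time and group-by-time model first and adjusted models second. They tie imbalance-driven covariates to baseline and never list sessions. Intent-to-treat is mentioned. Even if sessions entered as a main effect, the group-by-time test would not move.

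The last point stands, and it limits the concern. A reader might infer from the −r·d shift that the trial's main efficacy test is at risk: under d = 0.5 and r = 0.4 with the assumed trigger, a follow-up-only comparison of a true 0.38 averages 0.18 with 27% power, and rejects a true null 31% of the time. The documents do not support carrying those figures to the planned test. They describe a single-visit comparison with no baseline row, under invented inputs.

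A reader might also infer that the bias runs against CBT-I if that arm attends more. That needs sessions to correlate positively with benefit, and no document gives the sign for attendance or for delivery mode.

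The remaining defence is weaker. That the rule is exploratory has to be supplied by the reader. For paper versus electronic logs the protocol speaks of exploring possible effects; here it speaks of inclusion in analyses. Nor does the plan name group-by-time without sessions as the sole efficacy result, since it examines the group effect too.

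**Conclusion.** The concern holds as a point about what is estimated. Conditioning an arm comparison on session number or type does not give the effect of assignment, whatever the size of d, and the plan neither confines the rule to a supportive role nor says where it applies.

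The numerical harm is model-dependent and unknown. For group-by-time in the stated mixed model with a session main effect it is essentially nil: exactly nil for visit contrasts with complete data, and 0.001 in the dropout check. The group main effect would shift by 0.15 to 0.20 SD under the assumed inputs. A baseline-adjusted follow-up effect of 0.38 would fall to about 0.31 or 0.18, depending on whether sessions also relate to baseline. With the opposite sign of r × d, the shifts reverse. High pilot attendance, and make-ups within a week, suggest the rule may rarely be triggered.

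The tracked-characteristics sentence raises only a wording point. It points to Data Analysis, where imbalance-driven covariates are tied to baseline, so it is not evidence that later changes in hypnotic use or depression will be adjusted for.

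**What to change.** In the make-up session paragraph, replace the conditional inclusion with a statement that session number and type are not covariates in the efficacy or event-free survival arm comparisons. Report them by arm descriptively, or in an adherence analysis labelled supportive. Repeat the statement in the SAP, which is now silent.

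Optionally, add the word baseline to the tracked-characteristics sentence and to the covariate sentence for the multivariate models, to match the rule already in Data Analysis.

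The cost is a sentence or two and no new data. The downside is that adjustment for attendance or delivery mode becomes secondary, so an imbalance in delivery would be described and explored but would not alter the main estimate.
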